### 5.2.2.2. Male Mycotic Genital Infections

Balanitis and phimosis AEs will be identified using the MedDRA preferred terms listed in [Appendix 1.3](#), and the analyses will be based on the On-Treatment analysis set.

An overview summary table with the incidence and the exposure-adjusted incidence will be provided for:

- All AEs;
- Serious AEs;
- AEs considered drug-related (investigator assessment of possible, probable or very likely);
- AEs leading to discontinuation of study medication;
- Serious AEs leading to discontinuation of study medication;
- Serious AEs considered drug-related;
- AEs considered drug-related leading to discontinuation of study medication.

AEs by preferred term will be summarized by treatment group. A Kaplan-Meier plot for the time to first occurrence of balanitis will be provided by treatment group.

In addition, circumcision events will be identified using the sponsor's pharmacovigilance database and summarized by treatment group.

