9.4. Safety Evaluations

Safety and tolerability will be evaluated on the basis of the overall incidence of serious adverse events, adverse events that lead to study drug discontinuation, adverse events of interest, the incidence of MACE events (overall and within the first 30 days of study drug treatment), vital signs (pulse, blood pressure), and body weight. Adverse events that do not meet the definitions above will not be collected.

The safety data from this study will be combined with the data from the other large-scale study of the effects of canagliflozin compared to placebo (CANVAS) in a pre-specified meta-analysis of cardiovascular safety outcomes to meet regulatory requirements set at the time marketing authorization for canagliflozin was granted. The CV meta-analysis will be described in a separate document with a specific statistical analysis plan.

Serious Adverse Events and Adverse Events Leading to Discontinuation

Adverse events will be reported by the subject (or, when appropriate, by a caregiver, surrogate, or the subject's legally-acceptable representative) for the duration of the study, beginning from when informed consent is provided. Information about all adverse events (serious or not) should be recorded in source documents (eg, progress notes) according to good clinical practice, and retained at the investigative sites. Only serious adverse events, nonserious adverse events that result in study drug discontinuation, and adverse events of interest will be recorded on eCRFs.

For purposes of reporting serious adverse events for this study, nonfatal MI and nonfatal stroke events (ie, nonfatal MACE) will not immediately be subject to expedited serious adverse event reporting requirements. Refer to Section 12, Adverse Event Reporting, for details regarding the handling of MACE.

Collection of Additional Information for Adverse Events of Interest

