12.2. Procedures

12.2.1. All Adverse Events

For this study, all serious adverse events, nonserious adverse events that result in study drug discontinuation and other selected adverse events as specified later in this section are to be reported from the time a signed and dated informed consent form is obtained until completion of the study (including subjects who withdraw prematurely). For specific adverse events of interest, a supplemental eCRF page or other designated form will be used to collect additional information. Adverse events of interest include: all malignancies, fatal pancreatitis, hemorrhagic/necrotizing pancreatitis, severe hypersensitivity reactions (eg, angioedema, anaphylaxis, Stevens-Johnson syndrome), photosensitivity reactions, serious adverse events of hepatic injury, nephrotoxicity/acute kidney injury, venous thromboembolic events, fractures, male genital infections (balanitis, phimosis, events leading to circumcision), and pregnancy. Information on these events will be recorded on the supplemental eCRFs or other designated forms for any event that is serious or that leads to study drug discontinuation. In addition, non-serious adverse events of malignancies, photosensitivity reactions, fractures, amputations, and venous thromboembolic events will also be recorded on the supplemental CRF pages or other designated forms (in addition to the information collected on serious AEs and AEs leading to study drug discontinuation). Diabetic ketoacidosis has been designated an adverse event of special interest and therefore adverse events related to diabetic ketoacidosis, ketoacidosis, metabolic acidosis or acidosis need to be reported to Janssen within 24 hours of becoming aware of the event, which is the same timeframe for reporting of serious adverse events. These adverse events must be reported using a supplemental DKA Reporting form, to complement standard information collected on the eCRF AE/SAE page. Amputations have also been designated as adverse events of special interest and therefore amputations need to be reported to the sponsor within 24 hours of becoming aware of the event. If adverse events of interest are identified in the future, guidance concerning the reporting of those events may be provided to investigators via appropriately-documented study communications.

Data will be collected in source documents and on the eCRF for these adverse events.

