Serious adverse events, including those spontaneously reported to the investigator must be reported using a Serious Adverse Event Form, which must be completed and signed by a member of the investigational staff, and transmitted to the sponsor within 24 hours. The sponsor will evaluate any safety information that is spontaneously reported by an investigator beyond the time frame specified in the protocol.

Adverse events, regardless of severity or presumed relationship to study therapy, must be recorded using medical terminology in the source document and the eCRF. Whenever possible, diagnoses should be given when signs and symptoms are due to a common etiology (eg, cough, runny nose, sneezing, sore throat, and head congestion should be reported as “upper respiratory infection”). Investigators must record in the eCRF their opinion concerning the relationship of the adverse event to study therapy. All measures required for adverse event management must be recorded in the source document and reported according to sponsor instructions.

Study research staff should make study subjects aware of potential signs and symptoms of diabetic ketoacidosis such as difficulty breathing, nausea, vomiting, abdominal pain, feeling confused, fruity-smelling breath, and unusual fatigue or sleepiness. Study subjects should be instructed to contact the site if they experience such symptoms. If the investigator suspects these symptoms may be related to diabetic ketoacidosis (even if the subject’s blood glucose levels are less than 250 mg/dL [13.9 mmol/L]), testing for urine or blood ketones should be considered.

Consistent with standard diabetes treatment guidelines, all study participants should be provided with routine preventative foot care and early intervention for foot problems. Specifically:

- Provide or ensure that all subjects have had general foot self-care education.
- Perform a comprehensive foot evaluation at each visit to identify risk factors for ulcers and amputations. The examination should include inspection of the skin, assessment of foot deformities, neurological assessment including pinprick or vibration testing or assessment of ankle reflexes, and vascular assessment including pulses in the legs and feet.
- Subjects who have a history of prior lower extremity complications, loss of protective sensation, structural abnormalities, or peripheral arterial disease should be referred to foot care specialists for ongoing preventive care.

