**Table 3: Adverse Events of Interest**

**Section A: For the AEs listed below, only serious AEs or AEs that led to drug discontinuation were collected:**

- Osmotic diuresis
- Volume depletion
- Hypoglycemia
- Urinary tract infection (UTI)
- Female mycotic genital infection
- Severe hypersensitivity /cutaneous reactions
- Pancreatitis
- Hepatic injury
- Renal related AEs (including Nephrotoxicity/ acute kidney injury)

**Section B: The AEs listed below were collected regardless of whether they were serious and/or led to study drug discontinuation for the study:**

- Male mycotic genital infection (balanitis, phimosis, events leading to circumcision)
- Malignancy
  - Renal cell cancer
  - Bladder cancer
  - Pheochromocytoma
  - Leydig cell tumors
  - Breast cancer
- Photosensitivity
- Venous thromboembolic events (VTE)
- Amputation
- Fracture
- Diabetic Ketoacidosis

The AEs listed above will be identified using a MedDRA preferred term list ([Appendix 1.3](#)).

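### SAP 5.2.2.2 counts circumcisions from the pharmacovigilance database alone, though the related events were collected more widely on eCRFs, so non-serious cases may be missed

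*SAP*

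**What the plan says.** SAP 5.2.2.2 has two parts. For the infections it says "Balanitis and phimosis AEs will be identified using the MedDRA preferred terms listed in" Appendix 1.3, analysed in the On-Treatment set. For circumcision it turns to a different source, the sponsor's "pharmacovigilance database and summarized by treatment group". It names no second source, no reconciliation and no denominator for that summary.

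On collection, SAP 5.2.1 says that serious and non-serious events were both collected for the categories in Table 3 Section B. That section lists "Male mycotic genital infection (balanitis, phimosis, events leading to circumcision").

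Protocol 9.4 gives the general recording rule: "Only serious adverse events, nonserious adverse events that result in study drug discontinuation, and adverse events of interest will be recorded on eCRFs". Protocol 12.2.1 includes the same male genital category, with events leading to circumcision, among the adverse events of interest. For extra detail on such events it sets a narrower rule: information is "recorded on the supplemental eCRFs or other designated forms for any event that is serious or that leads to study drug discontinuation". The exception reads "non-serious adverse events of malignancies, photosensitivity reactions, fractures, amputations, and venous thromboembolic events will also be recorded on the supplemental CRF pages". Male genital infections are not in that exception.

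**The concern.** Circumcision is a clinically visible consequence of male genital infection on this drug class. Protocol 1.1.2 reports it in 17/3569 (0.5%) of men on canagliflozin and 3/1924 (0.2%) on control in the earlier program. Amendment INT-3 added the category, including events leading to circumcision, so that safety information on it would be collected.

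A count this small is sensitive to how cases are found. If the one source named in the SAP is narrower than the data the study collected, a few missed cases could change what the table shows. A reader of the table would also have no means of knowing.

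Other adverse events of interest are handled differently. SAP 5.2.2.3 summarises all malignancies from the supplementary page, and SAP 5.2.2.7 takes lower-extremity amputations from the dedicated case report form page. For circumcision the SAP names no study form.

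**Working it through.** No arithmetic applies, because the point concerns a data source. The check is whether each source or route in the documents would reach a circumcision that is neither serious nor a cause of stopping study drug.

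| Source or route | Where described | What it covers | Would it reach such a circumcision? |
|---|---|---|---|
| Pharmacovigilance database | SAP 5.2.2.2 | Content not described in either document | Unknown |
| Prompt reports to the sponsor | Protocol 12.2.1, 12.2.2, 12.2.3 | Serious events, DKA-related events, amputations, pregnancy | No route stated for it |
| Adverse event eCRF records | Protocol 9.4; SAP 5.2.1 and Table 3 Section B | Adverse events of interest, for this category whether or not serious | Yes, for the event leading to it |
| Supplemental eCRFs or other designated forms | Protocol 12.2.1 | Serious or discontinuing events, plus five categories of non-serious event | Not required for this category |
| Preferred-term search | SAP 5.2.2.2, Appendix 1.3 | Male mycotic infection and phimosis terms | Finds the infection, not the procedure |

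Step by step:

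1. SAP 5.2.2.2 relies on the first row alone.
2. Serious events have a defined path to the sponsor. Protocol 12.2.1 says they "must be reported using a Serious Adverse Event Form" and be sent within 24 hours. The other events with a 24-hour path are DKA-related events, amputations and pregnancy. Non-serious balanitis or phimosis is not among them.
3. A circumcision done without admission does not meet the hospitalization criterion in Protocol 12.1.1, so it need not be classed as serious on that ground.
4. The clinical database should hold the event leading to such a circumcision, under Protocol 9.4 and Table 3 Section B. SAP 5.2.2.2 does not use those records to count circumcisions.
5. The term lists cannot fill the gap. The male mycotic infection and phimosis lists in Appendix 1.3 contain no circumcision term, so the balanitis or phimosis would be counted and the circumcision would not.
6. The two documents also differ on this category. Table 3 Section B groups it with events collected regardless of seriousness. The protocol's exception for non-serious events on supplemental forms omits it. The two can coexist if the adverse event page takes every case and the supplemental form only some, but neither document says so.

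The proportion of circumcisions that might be missed cannot be derived. The documents give no split of circumcisions by seriousness, no description of what the pharmacovigilance database captures, and no number of men per arm.

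**The case against.** The strongest reply is that nothing in the documents shows the database to be incomplete. A reader might infer from the 24-hour routes that it is a serious-only source, and hence that circumcisions are undercounted. The documents do not support that step. They say how certain events are reported, not what the safety function holds. Other routes are open: Protocol 12.2.1 requires measures taken to manage an adverse event to be reported according to sponsor instructions, and it allows other designated forms. The seriousness definition in Protocol 12.1.1 also takes in important medical events and events judged to have significant clinical impact, so some circumcisions without admission may have been reported as serious. All of this stands, and it limits the finding to a risk.

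A reader might also infer that the protocol places non-serious cases on the supplemental pages. It does not, since that rule is limited for this category to serious or discontinuing events. The broader-collection argument rests on Protocol 9.4 and SAP Table 3 Section B.

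Nor should the program proportions be scaled to this trial to size the loss. The number of men per arm and the share captured would both be assumed, and SAP 5.2.2 says that incidences here are not comparable with those of the Phase 3 program. The four-subject threshold in SAP 5.2.2.1 decides which adverse events receive a confidence interval. It is not tied to the circumcision summary, which is reported whatever the count.

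Finally, the main analysis of male genital infection is intact: balanitis and phimosis are analysed from preferred terms, serious or not, and circumcision is an added descriptive count. That is correct and keeps the point minor. It does not answer why one source of undescribed content is used when the study holds other records of the same events.

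**Conclusion.** The point holds as a risk. The SAP names one source for circumcision and does not describe its content, although the plan says that the events leading to circumcision were collected more broadly on eCRFs. Non-serious circumcisions may be missed, and no other planned analysis would reveal the omission.

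The size of any undercount is unknown and cannot be calculated from the documents. The conclusion assumes that the routes set out in the protocol are a fair guide to how non-serious male genital infections reach the sponsor. If the database in fact captures non-serious cases, the count may be complete and only the description is lacking.

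The consequence is confined to one descriptive safety table. No hypothesis test, primary endpoint or secondary endpoint depends on it. This is a worthwhile improvement and not a defect that threatens the trial's conclusions.

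**What to change.** In SAP 5.2.2.2:

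- State what the pharmacovigilance database captures, in particular whether it includes non-serious male genital infections.
- Identify circumcisions from the union of that database, the adverse event eCRF records (including the reported terms for balanitis, phimosis and events leading to circumcision) and any supplemental or designated forms, reconciled per subject.
- Report them by treatment group among treated men, with the number found in each source.

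Separately, reconcile SAP Table 3 Section B with the protocol's rule that limits supplemental forms for male genital infections to serious or discontinuing events, and say which form carries the non-serious cases.

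The cost is a few sentences in the SAP and one reconciliation listing. No new data collection is needed. The limit is that a circumcision noted only in site source documents would still not be found, and the SAP should say so. If the database proves already to include non-serious cases, one sentence to that effect plus the listing closes the point.

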### 5.2.2.3. Selected Malignancies

The selected malignancies of interest are renal cell cancer, bladder cancer, testicular cancer (Leydig cell tumors), pheochromocytomas, and breast cancer. Selected malignancy AEs will be identified using the MedDRA Preferred terms listed in [Appendix 1.3](#), and the analyses will be based on the On-Study analysis set.

For each selected malignancy of interest, an overview summary table with the incidence and the follow-up-adjusted incidence will be provided for:

- All AEs;
- Serious AEs;
- AEs considered drug-related (investigator assessment of possible, probable or very likely);
- AEs leading to discontinuation of study medication;
- Serious AEs leading to discontinuation of study medication;
- Serious AEs considered drug-related;
- AEs considered drug-related leading to discontinuation of study medication.

The preferred terms associated with each selected malignancy type will be summarized by treatment.

A summary of all malignancy events as reported in the malignancy supplementary page will be reported by treatment and primary site. For breast, bladder, or renal cancers, the risk factors for each cancer type captured in the supplementary page will be summarized by treatment.

#### **5.2.2.4. Photosensitivity**

Photosensitivity AE will be identified using the MedDRA preferred terms listed in [Appendix 1.3](#), and the analyses will be based on the On-Treatment analysis set.

An overview summary table with the incidence and the exposure-adjusted incidence will be provided for:

- All AEs;
- Serious AEs;
- AEs considered drug-related (investigator assessment of possible, probable or very likely);
- AEs leading to discontinuation of study medication;
- Serious AEs leading to discontinuation of study medication;
- Serious AEs considered drug-related;
- AEs considered drug-related leading to discontinuation of study medication.

AEs by preferred term will be summarized by treatment group.

#### **5.2.2.5. Venous Thromboembolic Events**

Venous thromboembolic (VTE) events will be identified using the MedDRA preferred terms listed in [Appendix 1.3](#).

An overview summary table with the incidence and the exposure-adjusted incidence will be provided for:

- All AEs;
- Serious AEs;
- AEs considered drug-related (investigator assessment of possible, probable or very likely);
- AEs leading to discontinuation of study medication;
- Serious AEs leading to discontinuation of study medication;
- Serious AEs considered drug-related;
- AEs considered drug-related leading to discontinuation of study medication.

AEs by preferred term will be summarized by treatment group.

#### **5.2.2.6. Fracture**

Fracture events identified by the investigator or the sponsor for meeting the criteria pre-specified in the charter will be sent to the independent Fracture Adjudication Committee to confirm that

events were fractures and to determine fracture location (anatomic region) and type (low trauma or not). The main analyses of the adjudicated low trauma fracture AEs will be based on the On-Study analysis set.

An overview summary table with the incidence and the follow-up-adjusted incidence will be provided for:

- Adjudicated fractures;
- Adjudicated fractures considered serious (investigator assessment);
- Adjudicated fractures considered drug-related (investigator assessment of possible, probable or very likely);
- Adjudicated fractures leading to discontinuation of study medication;
- Adjudicated fractures considered serious and drug-related (investigator assessment);
- Adjudicated fractures considered drug-related (investigator assessment) and leading to discontinuation of study medication.

A summary of adjudicated fracture stratified by anatomical region by treatment will be provided. The incidence as well as the incidence rate will be presented.

Adjudicated AEs associated with fall will be summarized by treatment group.

A Kaplan-Meier plot for the time to the first occurrence of adjudicated fracture event will be provided by treatment group. The hazard ratio between canagliflozin (all canagliflozin) compared to placebo and its 95% confidence interval will be estimated from a Cox proportion hazards model with treatment as the explanatory variable.

A summary of all adjudicated fractures by anatomic location will be provided. The hazard ratio and its 95% CI as well as a Kaplan-Meier plot for the first occurrence of all adjudicated fractures will be provided using the same analysis as the adjudicated low trauma fractures.

#### **5.2.2.7. Amputation**

The main analysis of lower extremity amputations as documented in the dedicated case report form page will be based on the On-Study analysis set. An overview summary table with the incidence and the follow-up-adjusted incidence will be generated for:

- All lower limb amputations;
- Traumatic lower limb amputation;
- Atraumatic lower limb amputation.

Summary of anatomical region (toe, ankle, trans-metatarsal, below knee, above knee) of lower extremity atraumatic amputations will be reported by treatment group.

For atraumatic lower limb amputation, a Kaplan-Meier plot for the time to the first occurrence of event will be provided by treatment group.

For the post-treatment AEs that may be associated with amputation, groupings of selected MedDRA preferred terms used to identify events to be included in each of the following SOC categories are presented in [Appendix 1.4](#):

- Infections and Infestations;
- Vascular disorders;
- Nervous System disorders;
- Skin and subcutaneous tissue disorders;
- Osteomyelitis.

The selected preferred terms in infections and infestation are further split into “Reversible Infection” and “Irreversible Infections”. In addition, the preferred terms grouped under the MedDRA high level term of “skin and subcutaneous tissue ulcerations” are also of interest.

For each AE group listed above, the incidence of the respective preferred terms will be summarized by treatment group.

#### **5.2.2.8. Diabetic Ketoacidosis**

Diabetic ketoacidosis (DKA) and related AEs will be identified using the list of MedDRA terms in [Appendix 1.3](#). Adverse events identified by the investigator or the sponsor for meeting the criteria pre-specified in the charter will be sent to the independent DKA Adjudication Committee. The main analysis of the DKA events will be based on adjudicated events of DKA in the On-Study analysis set. Events occurring at any time post-randomization, regardless of the timing of the last dose of study medication, will be included. For the adjudicated DKA events, a table will summarize the incidence and the follow-up-adjusted incidence rate.

A listing of all DKA and related events identified by the sponsor’s medical monitoring team and the subset of these events that went for adjudication will be provided.

